4.1.9. Table 9. Primary Feasibility Endpoint – Acute Procedural Success (ITT population)

	ITT Population	
	N = XX	
	n/N (%)	[95% CI]
Acute Procedural Success*	XX/XX (XX.X%)	[XX% - XX%]

CONFIDENTIEL / CONFIDENTIAL

Toute reproduction ou distribution, totale ou partielle, de ce document, sans autorisation préalable de ICON PLC est interdite. Reproduction and distribution of this document, in whole or in part, is strictly forbidden without prior authorization from ICON PLC.

	STATISTICAL ANALYSIS PLAN	FARAPULSE PersAFOne SAP V1.0 PERSAFONE Page 41 /49
---	----------------------------------	--

4.1.10. Table 10. Primary Feasibility Endpoint – Acute Procedural Success (PP population)

PP Population		
N = XX		
	n/N (%)	[95% CI]
Acute Procedural Success*	XX/XX (XX.X%)	[XX% - XX%]

4.1.11. Table 11. Additional Endpoints

ITT Population		
N = XX		
	Mean±S.D.	
	Median (min, max) (Q1, Q3)	[95% CI]
Time to Therapeutic Failure (days)	XX±X XX (XX, XX) (XX, XX)	[XX - XX]
	n/N (%)	[95% CI]
Proportion of subjects with Early recurrence of atrial fibrillation (ERAF) by 90 days after the index procedure	XX/XX (XX.X%)	[XX% - XX%]
Proportion of all ablated pulmonary veins that are isolated at the Index Procedure using the study device	XX/XX (XX.X%)	[XX% - XX%]
Proportion of all ablated pulmonary veins isolated using the study device during the Index Procedure that remain isolated at the 75-day remapping procedure	XX/XX (XX.X%)	[XX% - XX%]

CONFIDENTIEL / CONFIDENTIAL

Toute reproduction ou distribution, totale ou partielle, de ce document, sans autorisation préalable de ICON PLC est interdite.
Reproduction and distribution of this document, in whole or in part, is strictly forbidden without prior authorization from ICON PLC.

	STATISTICAL ANALYSIS PLAN	FARAPULSE PersAFOne SAP V1.0 PERSAFONE Page 42 /49
---	----------------------------------	--

The proportion of attempted subjects that achieve Chronic CTI Success, defined as persistent bi-directional electrical block across the CTI assessed at the 75-day Remapping Procedure	XX/XX (XX.X%)	[XX% - XX%]
The proportion of attempted subjects that achieve Chronic Focal Success, defined as persistent electrical nonconductivity of all extra-PV tissue targeted for ablation in the Index Procedure, excluding the CTI	XX/XX (XX.X%)	[XX% - XX%]

4.1.12. Table 12. Secondary Safety Endpoints

	ITT Population N = XX	
	n/N (%)	[95% CI]
Primary Safety Endpoint (Early and Late Onset Composite Safety Endpoint) assessed at 7 days	XX/XX (XX.X%)	[XX% - XX%]
Total Early (within 30 days of Index or Remap Procedure)	XX/XX (XX.X%)	[XX% - XX%]
Death	XX/XX (XX.X%)	[XX% - XX%]
Myocardial infarction (MI)	XX/XX (XX.X%)	[XX% - XX%]
Persistent diaphragmatic paralysis	XX/XX (XX.X%)	[XX% - XX%]
Stroke	XX/XX (XX.X%)	[XX% - XX%]
Transient ischemic attack (TIA)	XX/XX (XX.X%)	[XX% - XX%]
Peripheral or organ thromboembolism	XX/XX (XX.X%)	[XX% - XX%]
Pericarditis	XX/XX (XX.X%)	[XX% - XX%]
Cardiac tamponade / perforation	XX/XX (XX.X%)	[XX% - XX%]
Vascular access complications requiring intervention	XX/XX (XX.X%)	[XX% - XX%]
Heart block	XX/XX (XX.X%)	[XX% - XX%]
Total Late (any time during follow-up through 12 months)	XX/XX (XX.X%)	[XX% - XX%]

CONFIDENTIEL / CONFIDENTIAL

Toute reproduction ou distribution, totale ou partielle, de ce document, sans autorisation préalable de ICON PLC est interdite.
Reproduction and distribution of this document, in whole or in part, is strictly forbidden without prior authorization from ICON PLC.

ICON	STATISTICAL ANALYSIS PLAN	FARAPULSE PersAFOne SAP V1.0 PERSAFONE Page 43 /49
-------------	----------------------------------	--

Pulmonary vein (PV) stenosis (> 70% diameter reduction from baseline)	XX/XX (XX.X%)	[XX% - XX%]
Atrio-esophageal fistula	XX/XX (XX.X%)	[XX% - XX%]
Device-Related Serious Adverse Events (SAEs)	XX/XX (XX.X%)	[XX% - XX%]
Procedure-Related Serious Adverse Events (SAEs)	XX/XX (XX.X%)	[XX% - XX%]
Stroke	XX/XX (XX.X%)	[XX% - XX%]
Transient Ischemic Attack (TIA)	XX/XX (XX.X%)	[XX% - XX%]
Cardioversion	XX/XX (XX.X%)	[XX% - XX%]
Arrhythmia-related (AF, AFL, AT) hospitalization	XX/XX (XX.X%)	[XX% - XX%]

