6.2 Secondary Safety Endpoints

1. The Primary Safety Endpoint assessed at 7 rather than 30 days
2. The proportion of subjects with a device- or procedure-related SAE
3. The proportion of subjects with stroke or TIA
4. The proportion of subjects requiring cardioversion
5. The proportion of subjects requiring an arrhythmia-related hospitalization

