IF (30≤ (EVENT DATE-PROCEDURE DATE IN **PROCEDURAL DATA FORM (PR)**) **OR** (30≤ (EVENT DATE-≤REMAPPING DATE IN **FOLLOW-UP 3D ELECTROANATOMICAL MAPPING FORM (RM)**) **AND** PRIMARY SAFETY ENDPOINT EVENT CRITERIA=' Death' **THEN** DEATH='Yes'
ELSE DEATH='No'

- Derived criteria "Myocardial infarction" will be defined as follows:

IF (30≤ (EVENT DATE-PROCEDURE DATE IN **PROCEDURAL DATA FORM (PR)**) **OR** (30≤ (EVENT DATE-REMAPPING DATE IN **FOLLOW-UP 3D ELECTROANATOMICAL MAPPING FORM (RM)**) **AND** PRIMARY SAFETY ENDPOINT EVENT CRITERIA=' Myocardial infarction' **THEN** Myocardial infarction='Yes'.

ELSE Myocardial infarction ='No'.

- Derived criteria "PV Stenosis" will be defined as follows:

IF (0≤ (EVENT DATE-PROCEDURE DATE IN **PROCEDURAL DATA FORM (PR)**) ≤360 **AND** PRIMARY SAFETY ENDPOINT EVENT CRITERIA=' PV Stenosis' **THEN** PV Stenosis ='Yes'.
ELSE PV Stenosis ='No'.

- Derived criteria "Diaphragmatic Paralysis" will be defined as follows:

IF (30≤ (EVENT DATE-PROCEDURE DATE IN **PROCEDURAL DATA FORM (PR)**) **OR** (30≤ (EVENT DATE-REMAPPING DATE IN **FOLLOW-UP 3D ELECTROANATOMICAL MAPPING FORM (RM)**) **AND** PRIMARY SAFETY ENDPOINT EVENT CRITERIA=' Diaphragmatic Paralysis' **THEN** Diaphragmatic Paralysis ='Yes'.
ELSE Diaphragmatic Paralysis ='No'.

- Derived criteria "AE fistula" will be defined as follows:

IF (0≤ (EVENT DATE-PROCEDURE DATE IN **PROCEDURAL DATA FORM (PR)**) ≤360 **AND** PRIMARY SAFETY ENDPOINT EVENT CRITERIA=' AE fistula' **THEN** AE fistula ='Yes'.
ELSE AE fistula ='No'.

- Derived criteria "TIA" will be defined as follows:

IF (30≤ (EVENT DATE-PROCEDURE DATE IN **PROCEDURAL DATA FORM (PR)**) **OR** (30≤ (EVENT DATE-REMAPPING DATE IN **FOLLOW-UP 3D ELECTROANATOMICAL MAPPING FORM (RM)**) **AND** PRIMARY SAFETY ENDPOINT EVENT CRITERIA=' TIA' **THEN** TIA=Yes.
ELSE TIA='No'.

- Derived criteria "CVA" will be defined as follows:

CONFIDENTIEL / CONFIDENTIAL

Toute reproduction ou distribution, totale ou partielle, de ce document, sans autorisation préalable de ICON PLC est interdite.
Reproduction and distribution of this document, in whole or in part, is strictly forbidden without prior authorization from ICON PLC.

	STATISTICAL ANALYSIS PLAN	FARAPULSE PersAFOne SAP V1.0 PERSAFONE Page 27 /49
---	----------------------------------	--

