ELSE New or Prolonged Hospitalization, excl. AF/AFL ='No'

CONFIDENTIEL / CONFIDENTIAL

Toute reproduction ou distribution, totale ou partielle, de ce document, sans autorisation préalable de ICON PLC est interdite.
Reproduction and distribution of this document, in whole or in part, is strictly forbidden without prior authorization from ICON PLC.

	STATISTICAL ANALYSIS PLAN	FARAPULSE PersAFOne SAP V1.0 PERSAFONE Page 28 /49
---	----------------------------------	--

- Derived criteria “Vascular Access Complication” will be defined as follows:
IF (30≤ (EVENT DATE-PROCEDURE DATE IN PROCEDURAL DATA FORM (PR)) **OR** (30≤ (EVENT DATE-REMAPPING DATE IN FOLLOW-UP 3D ELECTROANATOMICAL MAPPING FORM (RM)) **AND** PRIMARY SAFETY ENDPOINT EVENT CRITERIA=’ Vascular Access Complication’ **THEN** Vascular Access Complication =’Yes’
ELSE Vascular Access Complication =’No’
- Derived criteria “Total Early and Late Onset Composite Safety Endpoint” will be defined as follows:
IF Death=Yes **OR** Myocardial infarction =Yes **OR** PV Stenosis =Yes **OR** Diaphragmatic Paralysis =Yes **OR** AE fistula =Yes **OR** TIA =Yes **OR** CVA=Yes **OR** Major pericarditis =Yes **OR** Tamponade/Perforation =Yes **OR** Pneumothorax =Yes **OR** Heart Block =Yes **OR** Pulmonary Edema =Yes **OR** New or Prolonged Hospitalization, excl. AF/AFL =Yes **OR** Vascular Access Complication =Yes **THEN** Total Early and Late Onset Composite Safety Endpoint =’Yes’
ELSE Total Early and Late Onset Composite Safety Endpoint =’No’
- Derived criteria “Total Early Onset Composite Safety Endpoint” will be defined as follows:
IF Death=Yes **OR** Myocardial infarction =Yes **OR** Diaphragmatic Paralysis =Yes **OR** TIA =Yes **OR** CVA=Yes **OR** Major pericarditis =Yes **OR** Tamponade/Perforation =Yes **OR** Heart Block =Yes **OR** New or Prolonged Hospitalization, excl. AF/AFL =Yes **OR** Vascular Access Complication =Yes **THEN** Total Early Onset Composite Safety Endpoint=’Yes’
ELSE Total Early Onset Composite Safety Endpoint=’No’
- Derived criteria “Total Late (any time during follow-up through 12 months)” will be defined as follows:
IF PV Stenosis =Yes **OR** AE fistula =Yes **THEN** Total Late (any time during follow-up through 12 months) =’Yes’
ELSE Total Late (any time during follow-up through 12 months) =’No’.

Secondary Safety endpoint

- Derived criteria “Death 7 days” will be defined as follows:

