IF (7≤ (EVENT DATE-PROCEDURE DATE IN PROCEDURAL DATA FORM (PR)) **OR** (7≤ (EVENT DATE-REMAPPING DATE IN FOLLOW-UP 3D ELECTROANATOMICAL MAPPING FORM (RM)) **AND** PRIMARY SAFETY ENDPOINT EVENT CRITERIA=’ Death’ **THEN** DEATH=’Yes’
ELSE DEATH=’No’
- Derived criteria “Myocardial infarction 7 days” will be defined as follows:
IF (7≤ (EVENT DATE-PROCEDURE DATE IN PROCEDURAL DATA FORM (PR)) **OR** (7≤ (EVENT DATE-REMAPPING DATE IN FOLLOW-UP 3D ELECTROANATOMICAL MAPPING FORM (RM)) **AND** PRIMARY SAFETY ENDPOINT EVENT CRITERIA=’ Myocardial infarction’ **THEN** Myocardial infarction=’Yes’.
ELSE Myocardial infarction = ‘No’.
- Derived criteria “Diaphragmatic Paralysis 7 days” will be defined as follows:

CONFIDENTIEL / CONFIDENTIAL

Toute reproduction ou distribution, totale ou partielle, de ce document, sans autorisation préalable de ICON PLC est interdite.
Reproduction and distribution of this document, in whole or in part, is strictly forbidden without prior authorization from ICON PLC.

	STATISTICAL ANALYSIS PLAN	FARAPULSE PersAFOne SAP V1.0 PERSAFONE Page 29 /49
---	----------------------------------	--

IF (7≤ (EVENT DATE-PROCEDURE DATE IN PROCEDURAL DATA FORM (PR)) **OR** (7≤ (EVENT DATE-REMAPPING DATE IN FOLLOW-UP 3D ELECTROANATOMICAL MAPPING FORM (RM)) **AND** PRIMARY SAFETY ENDPOINT EVENT CRITERIA=' Diaphragmatic Paralysis' **THEN** Diaphragmatic Paralysis ='Yes'.
ELSE Diaphragmatic Paralysis ='No'.

- Derived criteria "TIA 7 days" will be defined as follows:

IF (7≤ (EVENT DATE-PROCEDURE DATE IN PROCEDURAL DATA FORM (PR)) **OR** (7≤ (EVENT DATE-REMAPPING DATE IN FOLLOW-UP 3D ELECTROANATOMICAL MAPPING FORM (RM)) **AND** PRIMARY SAFETY ENDPOINT EVENT CRITERIA=' TIA' **THEN** TIA='Yes'.
ELSE TIA='No'.

- Derived criteria "CVA 7 days" will be defined as follows:

IF (7≤ (EVENT DATE-PROCEDURE DATE IN PROCEDURAL DATA FORM (PR)) **OR** (7≤ (EVENT DATE-REMAPPING DATE IN FOLLOW-UP 3D ELECTROANATOMICAL MAPPING FORM (RM)) **AND** PRIMARY SAFETY ENDPOINT EVENT CRITERIA=' CVA' **THEN** CVA='Yes'.
ELSE CVA='No'.

- Derived criteria "Major pericarditis 7 days" will be defined as follows:

IF (7≤ (EVENT DATE-PROCEDURE DATE IN PROCEDURAL DATA FORM (PR)) **OR** (7≤ (EVENT DATE-REMAPPING DATE IN FOLLOW-UP 3D ELECTROANATOMICAL MAPPING FORM (RM)) **AND** PRIMARY SAFETY ENDPOINT EVENT CRITERIA=' Major pericarditis' **THEN** Major pericarditis = 'Yes'.
ELSE Major pericarditis = 'No'.

- Derived criteria "Tamponade/Perforation 7 days" will be defined as follows:

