IF (7≤ (EVENT DATE-PROCEDURE DATE IN PROCEDURAL DATA FORM (PR)) **OR** (7≤ (EVENT DATE-REMAPPING DATE IN FOLLOW-UP 3D ELECTROANATOMICAL MAPPING FORM (RM)) **AND** PRIMARY SAFETY ENDPOINT EVENT CRITERIA=' Vascular Access Complication' **THEN** Vascular Access Complication = 'Yes'.
ELSE Vascular Access Complication = 'No'.
- Derived criteria "Total Early Onset Composite Safety Endpoint assessed at 7 days" will be defined as follows:
IF Death 7 days='Yes' **OR** Myocardial infarction 7 days='Yes' **OR** Diaphragmatic Paralysis 7 days='Yes' **OR** TIA 7 days='Yes' **OR** CVA 7 days='Yes' **OR** Major pericarditis 7 days='Yes' **OR** Tamponade/Perforation 7 days='Yes' **OR** Heart Block 7 days='Yes' **OR** New or Prolonged Hospitalization, excl. AF/AFL 7 days='Yes' **OR** Vascular Access Complication 7 days='Yes' **THEN** Total Early Onset Composite Safety Endpoint assessed at 7 days = 'Yes'.
ELSE Total Early Onset Composite Safety Endpoint assessed at 7 days = 'No'.
- Derived criteria "Device-Related Serious Adverse Events (SAEs)" will be defined as follows:
IF CEC seriousness ="Serious" **AND** CEC relationship to study Device in (Causal relationship, Probably related, Possibly related, Unlikely to be related) in adverse event adjudication form **THEN** Device-Related Serious Adverse Events (SAEs)='Yes'; **ELSE** Device-Related Serious Adverse Events (SAEs)='No'
- Derived criteria "Procedure-Related Serious Adverse Events (SAEs)" will be defined as follows:
IF CEC relationship to study procedure in (Causal relationship, Probably related, Possibly related, Unlikely to be related) **AND** CEC seriousness ='Serious' **THEN** Procedure-Related Serious Adverse Events (SAEs)='Yes'
ELSE IF CEC relationship to study procedure ='Not related' **AND** CEC seriousness =" Serious" **THEN** Procedure-Related Serious Adverse Events (SAEs)='No'
- Derived criteria "Cardioversion" will be defined as follows:
IF Arrhythmia-Treatment DC Cardioversion is ticked in **Arrhythmia episodes form** **THEN** Cardioversion ='Yes';
ELSE Cardioversion ='No'

CONFIDENTIEL / CONFIDENTIAL

Toute reproduction ou distribution, totale ou partielle, de ce document, sans autorisation préalable de ICON PLC est interdite.
Reproduction and distribution of this document, in whole or in part, is strictly forbidden without prior authorization from ICON PLC.

	STATISTICAL ANALYSIS PLAN	FARAPULSE PersAFOne SAP V1.0 PERSAFONE Page 31 /49
---	----------------------------------	--

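### SAP Table 12 labels the 7-day safety endpoint's early rows as 30-day and gives it an early-plus-late headline that no 7-day derivation in SAP 2.5 supports

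*SAP*

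**What the plan says.** Protocol 6.2 and SAP 2.4.8.2 define the first secondary safety endpoint in the same words: "The Primary Safety Endpoint assessed at 7 rather than 30 days". Neither says what happens to late-onset events. In the primary endpoint (Protocol 6.1, SAP 2.4.8.1), the 30-day window belongs to the early-onset list only. Pulmonary vein stenosis and atrio-esophageal fistula count at any time up to 12 months.

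SAP 2.5 derives a set of 7-day variables for early components and one 7-day total, "Total Early Onset Composite Safety Endpoint assessed at 7 days". That total has no stenosis or fistula term. The only composite in SAP 2.5 that joins early and late events is "Total Early and Late Onset Composite Safety Endpoint", which belongs to the primary endpoint.

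The Table 12 shell (SAP 4.1.12) opens with "Primary Safety Endpoint (Early and Late Onset Composite Safety Endpoint) assessed at 7 days". Beneath it stand an early subtotal, "Total Early (within 30 days of Index or Remap Procedure", with ten component rows, and a late subtotal, "Total Late (any time during follow-up through 12 months", with stenosis and fistula. The subtotal and component labels are those of Table 8.

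**The concern.** One block carries three windows (7 days, 30 days, 12 months), and its headline has no rule behind it. A programmer could fill the headline from the primary composite, which is not a 7-day result, or print the early-only 7-day total under a label that promises late events too. In the first case the number is wrong for the row, and in the second the label is wrong for the number. The 7-day total that is derived has no row of its own.

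The study is descriptive, with no hypothesis test (Protocol 5.3, SAP 2.2). The reported proportion and its interval are the whole result for this endpoint, so a wrong window label misstates what was found.

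**Working it through.** The documents state no rate, power or sample size for this endpoint, so there is no figure to reproduce. The check compares table rows with derivations, then windows, then the weight of one event.

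**1. Table 12 against SAP 2.5**

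| Table 12 row | Window in its label | Matching 7-day rule in SAP 2.5 |
|---|---|---|
| Headline, early and late | 7 days | None; the 7-day total is early-onset only |
| Early subtotal | 30 days | A 7-day early total exists, so the label disagrees |
| Early components | 30 days, through the subtotal | 7-day variables exist, except for peripheral or organ thromboembolism |
| Late subtotal, stenosis, fistula | 12 months | None; the primary endpoint's rules run to day 360 ("≤360 AND PRIMARY SAFETY ENDPOINT EVENT CRITERIA=' PV Stenosis") |

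**2. Both readings of the endpoint**

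- *Early events only, to 7 days.* The SAP 2.5 total has the right scope. The Table 12 headline, early label and late rows are wrong.
- *Early events to 7 days plus late events to 12 months.* The headline's scope and the late rows are right. The early label is still wrong, and SAP 2.5 lacks the composite.

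Table and derivation conflict under both, and the 30-day label is wrong under both.

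**3. How far the windows differ**

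Take remap at day 60, 75 or 90 (75 ± 15) and count whole days from 0.

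- 7-day early window: 8 days after each of two procedures, 2 × 8 = 16 days per subject. It ends on day 60 + 7 = 67, 75 + 7 = 82 or 90 + 7 = 97.
- 30-day early window: 2 × 31 = 62 days, ending on day 90, 105 or 120.
- Excess admitted by the 30-day label: 62 − 16 = 46 days per subject.
- Late events under the primary rule: to day 360.

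**4. The 7-day component rule as written**

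Each rule begins "7≤ (EVENT DATE-PROCEDURE DATE IN PROCEDURAL DATA FORM (PR", with an alternative of the same form for the remap and no upper bound. Read literally, it admits day 7 to day 395 (365 + 30, the end of the 12-month visit window) and drops days 0 to 6 after the index procedure. The remap clause adds nothing, because any day at least 7 days after the remap is also at least 7 days after the index procedure. Of the 16 intended days it keeps 9: day 7 and the 8 days from the remap onward. It admits 389 days in all (395 − 7 + 1), so 389 − 9 = 380 lie outside the intended window.

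**5. Components of the 7-day total**

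Against the early-onset list in Protocol 6.1, the SAP 2.5 total adds new or prolonged hospitalization and omits peripheral or organ thromboembolism. Table 12 has a thromboembolism row but no hospitalization row.

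**6. Weight of one event**

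N = 40 is the planned maximum (Protocol 3.7). Some SAP shells (Tables 5 and 19) print N = 25, so both are shown.

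- One event: 1/40 = 2.5 points, or 1/25 = 4.0 points.
- 0/40: SAP 2.1.4 prescribes Agresti-Coull at 0% if the asymptotic conditions fail. With z² = 3.84, the adjusted n is 43.84 and the adjusted proportion is 1.92/43.84 = 0.0438. The upper limit is 0.0438 + 1.96 × √(0.0438 × 0.9562/43.84) = 0.104, or 10.4%.
- 1/40 = 2.5%, exact 95% interval 0.1 to 13.2%.
- 2/40 = 5.0%, exact 95% interval 0.6 to 16.9%.

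**The case against.** The strongest reply is that the late rows may be intended. Only the early list has a 30-day window, so putting 7 in place of 30 can mean a shorter early window with late events kept to 12 months. That reading is fair. A reader might infer that any event counted up to month 12 under a 7-day heading is an error, or that the endpoint exists to isolate acute complications. The documents support neither: they state no such purpose and leave the late events open. This reply does not rescue the early label or supply the missing derivation.

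A second reply is that the programmer would fill the early rows from the 7-day variables in SAP 2.5, which evidently exist for this table, and that the labels are carried-over text. This is plausible for most rows, so a literal repeat of Table 8 is a worst case and not the expected outcome. It leaves the printed label wrong, the headline without a rule, and the thromboembolism row without a 7-day variable.

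Third, the endpoint is secondary and descriptive, and the shell shows late events on separate rows, so a careful reader could separate them. That limits the severity but does not remove the conflict.

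**Conclusion.** The point holds as a conflict between table and derivation. Under either reading of the endpoint, Table 12's early label is wrong and its headline does not match the 7-day total in SAP 2.5. The documents do not support the stronger claim that late events must be excluded, and the choice is the sponsor's to state.

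The size is illustrative because no event rate is given. Each misplaced event moves the reported rate by 2.5 points if 40 subjects are analysed. The interval limits assume that the asymptotic conditions in SAP 2.1.4 fail at such low counts. Correcting the labels alone would not give a 7-day rate, because the component rules as written do not select days 0 to 7. The change should be made before the tables are produced, as a correction to a secondary descriptive endpoint.

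**What to change.** 1. In Table 12, relabel the early subtotal and its component rows as within 7 days of the index or remap procedure, and fill them from the 7-day variables.
2. State in the SAP whether late-onset events count in this endpoint. Then either (a) make the headline the early-only 7-day composite and drop the late rows from this block, where they would remain in Table 8; or (b) keep the headline and late rows, and add a derivation for early events to 7 days plus late events to 12 months.
3. In SAP 2.5, make each 7-day rule select events from day 0 to day 7 after the index or remap procedure.
4. Match the 7-day composite to the protocol's list: add peripheral or organ thromboembolism, with its own 7-day variable, and remove new or prolonged hospitalization.

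The cost is one edited table shell and minor changes to the derivations; option (b) adds one composite rule. No new data should be needed, assuming the adjudication form records thromboembolism as a category, which the documents do not show.

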4.1.13. Table 13. Secondary Feasibility Endpoints

	ITT Population	
	N = XX	[95% CI]
Chronic Procedural Success (CPS)* for subjects who undergo the protocol-specified 75-Day Remapping Procedure	XX/XX (XX.X%)	[XX% - XX%]
Acute Cavotricuspid isthmus (CTI) Success**	XX/XX (XX.X%)	[XX% - XX%]
Therapeutic Success***	XX/XX (XX.X%)	[XX% - XX%]
On AADs	XX/XX (XX.X%)	[XX% - XX%]
Off AADs	XX/XX (XX.X%)	[XX% - XX%]
Durability of the CTI and/or other extra PV lesion set(s)	XX/XX (XX.X%)	[XX% - XX%]

4.1.14. Table 14. Adverse Events (AEs) (not including SAEs)

SOC Term/PT Term	ITT Population		
	Total Number of	Number of	n/N (%)

CONFIDENTIEL / CONFIDENTIAL

Toute reproduction ou distribution, totale ou partielle, de ce document, sans autorisation préalable de ICON PLC est interdite.
Reproduction and distribution of this document, in whole or in part, is strictly forbidden without prior authorization from ICON PLC.

ICON	STATISTICAL ANALYSIS PLAN	FARAPULSE PersAFOne SAP V1.0 PERSAFONE Page 44 /49
-------------	----------------------------------	--

	Events	patients n	[95% CI]
ALL	XX	XX	XX/XX (XX.X%) [XX% - XX%]
SOC1	XX	XX	XX/XX (XX.X%) [XX% - XX%]
PT1	XX	XX	XX/XX (XX.X%) [XX% - XX%]
PT2	XX	XX	XX/XX (XX.X%) [XX% - XX%]
SOC2	XX	XX	XX/XX (XX.X%) [XX% - XX%]
PT3	XX	XX	XX/XX (XX.X%) [XX% - XX%]
PT4	XX	XX	XX/XX (XX.X%) [XX% - XX%]

4.1.15. Table 15. Serious Adverse Events (SAEs)

SOC Term/PT Term	ITT Population		
	Total Number of Events	Number of patients n	n/N (%) [95% CI]
ALL	XX	XX	XX/XX (XX.X%) [XX% - XX%]
SOC1	XX	XX	XX/XX (XX.X%) [XX% - XX%]
PT1	XX	XX	XX/XX (XX.X%) [XX% - XX%]
PT2	XX	XX	XX/XX (XX.X%) [XX% - XX%]
SOC2	XX	XX	XX/XX (XX.X%) [XX% - XX%]
PT3	XX	XX	XX/XX (XX.X%) [XX% - XX%]
PT4	XX	XX	XX/XX (XX.X%) [XX% - XX%]

CONFIDENTIEL / CONFIDENTIAL

Toute reproduction ou distribution, totale ou partielle, de ce document, sans autorisation préalable de ICON PLC est interdite.
Reproduction and distribution of this document, in whole or in part, is strictly forbidden without prior authorization from ICON PLC.

	STATISTICAL ANALYSIS PLAN	FARAPULSE PersAFOne SAP V1.0 PERSAFONE Page 45 /49
---	----------------------------------	--

